7. SELECTION AND ENROLLMENT OF SUBJECTS

Inclusion criteria:

- Postmenopausal women who are diagnosed with osteoporosis either by a DXA scan with a T score <-2.5 either by suffering a low intensity fracture (even in the absence of a DXA scan with T score <-2.5). The bone location that will be used in this study – lumbar spine- is among the recommended for evaluation of BMD by bone densitometry.
- Written informed consent

Exclusion criteria:

- Previous treatment with drugs that modify bone metabolism
- Renal failure (GFR <35 ml/min, as suggested by drug spc)
- History of reflux esophagitis, gastric or duodenal ulcers, gastrectomy

- Bone disease such as primary hyperparathyroidism, hyperthyroidism, Paget disease, Cushing syndrome, multiple myeloma, rheumatoid arthritis, or osteogenesis imperfecta.

Enrollment:

Patient pool will comprise of all patients attending the orthopaedic clinic of Larisa Public Hospital. The first 512 patients assessed in this clinic and recommended based on national guidelines and international good clinical practice that they need to be treated with biphosphonates, will be candidates to be enrolled in this study. All patients must sign the appropriate consent form before being enrolled into the study.

8. TREATMENT PROCEDURES AND STUDY PROCEDURES

This study is designed to follow and observe patients who will initiate treatment with Alendronate 70mg in routine clinical practice. No study-specific treatment will be provided and no additional clinical procedures or assessments will be required as part of this observational study. Patients will be observed for a period of up to 12 months after their entry in the study unless patients discontinue the study or are lost to follow up. Information regarding the clinical management of the patients receiving Alendronate 70mg may be collected whenever available, even after treatment discontinuation.

There are no procedures or changes to routine clinical management of patients. It is anticipated that patients will return to the clinic every month to receive their Alendronate 70mg prescription. Patients will be followed for approximately 6 months after their last visit. Available clinical information obtained for routine clinical practice (including those already recorded on the patient medical records ie, baseline characteristics) will be recorded, including Alendronate 70mg administration, previous and current therapies, medical history (including fracture history), ADRs and serious ADRs and co-morbidities.

Throughout the study, investigators may prescribe any concomitant medications or treatments deemed necessary to provide adequate routine clinical care including calcium and vitamin D supplementation, which will be recorded.

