4. STUDY OBJECTIVES

Primary objective:

Evaluate Bone Mineral Density (BMD) changes at lumbar spine of Greek osteoporotic women from baseline to 12th month from the initiation of Alendronate 70mg once weekly.

Secondary objectives:

Evaluate new vertebral and non-vertebral fragility fractures, hip fractures, treatment compliance, occurrence of back pain and days lost from work due to fracture related back pain from baseline to 12th month from the initiation of Alendronate 70mg once weekly.

Also evaluate the safety of Alendronate assessed by the type, frequency, and severity of ADRs for 18 months after the initiation of study.

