6. STUDY DESIGN

This is a Greek observational prospective study to evaluate the effect of a biphosphonate drug, Alendronate, on BMD in postmenopausal women for a total period of 12 months. This observational study will not alter the routine clinical management of patients and will comply with all applicable local regulations of Greece. The decision to treat the patient with Alendronate must be made independent of and prior to their enrollment in the study. It is expected that patients eligible to participate will receive their first prescription during their initial clinic appointment and thereafter once monthly along with local standard clinical care according to clinical judgment and international guidelines. Approximately 512 patients will be enrolled in the study. The first 512 patients that will attend the orthopaedic clinic of Larisa Public Hospital and will be deemed appropriate candidates for biphosphonates treatment will be eligible to participate in the study. Detailed data obtained as part of routine clinical practice will be collected at the initial visit directly from patients or through their past medical record. These will comprise of demographic patient data, medical condition, risk factors for osteoporosis, and comorbidities. It is anticipated that patients will return to the clinic every month to receive their Alendronate prescription and record protocol adherence. After the initial visit, information regarding Alendronate prescription and administration, concomitant medication use, and non-serious and serious ADRs will be obtained during monthly clinical visits and recorded for up to approximately 6 months after completion of the study, a period that is thought appropriate to document ADRs and serious ADRs.

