10. STATISTICAL CONSIDERATIONS

Study Outcomes:

The following outcomes are to characterize/estimate the effectiveness during the first 12 months of treatment with Alendronate.

Primary outcome:

- BMD change (%) at lumbar spine at 6,12 months of treatment measured by DXA

Secondary outcomes:

- the proportion of patients with severe osteoporosis experiencing one or more new vertebral and non-vertebral fragility fractures assessed by spine radiographs regardless of symptoms
- Compliance to therapy, self-reported by patients
- Days lost from work due to fracture-related back pain, self reported by patients

The following secondary outcomes are to characterize the safety of patients during the first 12 months of treatment with Alendronate and during the 6 month follow up period:

- the proportion of patients with ADR to Alendronate
- the proportion of patients with serious ADR to Alendronate

The Full Analysis Set will consist of all enrolled patients satisfying the inclusion/exclusion criteria that receive at least 46 doses - 96% of the 48 that ideally would receive during the study duration- and have a non-missing enrollment date. All analyses will be performed on this analysis set.

Subsets and/or Covariates:

The following variables will be collected at baseline, either directly as part of routine clinical practice, or from medical records when available:

Demographic patient data:

- Educational level
- Patient employment status
- Patient living situation (at home with spouse/family, at home with care/support, at home alone, nursing home)

Medical condition regarding osteoporosis:

- Body mass index (≤ 25 or > 25 kg/m²)
- Age at menopause
- Cause of menopause (natural onset, clinically/surgically induced)
- Height loss since maximal height
- Height loss in centimeters (cm)
- Previous fracture
 - Previous hip fracture
 - Previous vertebral fracture
 - Other previous fractures
- Previous hospitalization for osteoporotic fracture and/or surgical osteoporotic fracture treatment
- One or more falls experienced during the past 12 months
- One or more episodes of immobility experienced during the past 12 months
- Parent fractured hip
- Current smoker
- Former smoker
- Systemic glucocorticoid use
- Secondary osteoporosis
- Alcohol consumption
- Femoral neck BMD T-score
- Lumbar spine BMD T-score
- Total hip BMD T-score

Patient-related:

- Age (years)
- Age group (< 65, ≥ 65 to <75, ≥ 75 years)
- Time since Post Menopausal Osteoporosis (PMO) diagnosis

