- Number of comorbidities
- Any chronic medical condition
- Type of chronic medical condition (diabetes/osteoporosis/hypertension/other)

Sample Size:

A review of published data highlighted that BMD change at lumbar spine at 12 months for postmenopausal women on alendronate 70mg weekly ranges from 3.7%-5.1%.¹³⁻¹⁵

Taking into account the most unfavourable result, which is 5.1%, we will estimate the sample size of our study. We will conduct an observational study which intends to investigate the Lumbar Spine BMD (%) change from baseline to 12 months (single proportion).

Published data estimate that Lumbar Spine BMD increases 5.1% from baseline to 12 months.

We would like to ensure that 95% CI of the Lumbar Spine BMD change (%) is estimated with precision ±2% (i.e. with a margin of error of 2%).

The required sample size would be $n \geq \frac{z^2}{\delta^2} p(1-p) \rightarrow n \geq \frac{1.96^2}{0.02^2} 0.051(1-0.051) \rightarrow n \geq 465$

If we add 10% to compensate for potential loss of subjects, the final number will sum up to $n \geq 512$ patients.

Thus in order to have sufficient precision and compensate for potential loss of subjects the final sample size should be 512 patients.

Data Analyses

This is an observational study for which the analysis will be descriptive in nature and no formal hypothesis will be tested. T test will be used to assess the change in BMD between baseline and end of study measurements. Significance was indicated at $P < 0.05$.

For quantitative parameters (BMD, days lost from work) mean, standard deviation, median, range (minimum and maximum), as well as number of missing data (if relevant) will be displayed. For qualitative parameters (bone fractures) counts, percentages and number of missing data if relevant will be displayed. Treatment compliance for each patient will be calculated as the number of doses study drug was actually taken, with the maximum count being 48. Compliance will be regarded as a quantitative parameter.

In general, missing values will remain as missing, i.e., no attempt will be made to impute missing values and only observed values will be used in data analyses and presentations.

Baseline characteristics will be described. Demographics, medical history and other baseline variables will be summarized as appropriate to the type of data.

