11. SAFETY DATA SELECTION AND ADVERSE EXPERIENCE REPORTING

Adverse Drug Reaction

Definition of Adverse Drug Reaction: An Adverse Drug Reaction (ADR) is defined as an adverse event associated with a given medication at normal dosage. The definition of adverse events includes worsening of a pre-existing medical condition. Worsening indicates the pre-existing medical condition (eg, diabetes, migraine headaches, gout) has increased in severity, frequency, and/or duration, and/or has an association with a significantly worse outcome. A pre-existing condition that has not worsened during the study, and involves an intervention such as elective cosmetic surgery or a medical procedure while on study is not considered an adverse event. The Investigator should specify the date of onset, intensity, action taken with respect to Alendronate, corrective treatment/therapy given, outcome and his/her opinion as to whether there is a reasonable possibility that the Adverse Event was caused by Alendronate.

Lab, vital signs, or ECG abnormalities are to be recorded as adverse events only if they are medically relevant: symptomatic, require corrective treatment, lead to study drug discontinuation and/or fulfill a seriousness criterion. In that case the procedure imposed by the event of a serious adverse drug reaction (SADR) should be followed.

Reporting Procedures for Adverse Drug Reactions: The investigator is responsible for ensuring that all ADRs to Alendronate 70mg observed by the investigator or reported by the patient that occur after the first administration of Alendronate through the end of study and through the following 6 months are captured. The investigator must assess whether any adverse event is possibly related to Alendronate 70mg and if that is the case he should proceed by recording the ADR and assign the following ADR attributes:

- ADR diagnosis or syndrome(s), if known (if not known, signs or symptoms),
- Date(s) of onset and resolution,
- Severity, and
- Action taken.

Serious Adverse Drug Reaction

Definition of Serious Adverse Drug Reaction: A SADR is a serious adverse event that is considered related to the medicinal product. A serious adverse event is defined as an adverse event that meets at least 1 of the following serious criteria:

- fatal
- life threatening (places the patient at immediate risk of death)
- requires in-patient hospitalization or prolongation of existing hospitalization

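### Women who stop alendronate stay under observation, but the protocol fixes no way to obtain their fracture and ADR data to months 12 and 18

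*Protocol*

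**What the plan says.** **Time frame.** Section 4 sets BMD, fractures, back pain and days lost from work "from baseline to 12th month from the initiation of Alendronate 70mg once weekly", and ADRs over 18 months. Neither depends on staying on the drug. Sections 1 and 10 word the primary outcome differently: "BMD change (%) at lumbar spine at 6,12 months of treatment measured by DXA".

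**Who is still in the study.** Under Section 8, observation for up to 12 months ends early only if the patient discontinues the study or is lost to follow-up. Section 9 deals with withdrawal from the study. Stopping the drug is not named as an end of observation in either section.

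**How data are obtained.** Section 6 expects that "patients will return to the clinic every month to receive their Alendronate prescription and record protocol adherence", and says ADR information comes from these monthly visits. Section 8 repeats: "It is anticipated that patients will return to the clinic every month to receive their Alendronate 70mg prescription". It adds that "no additional clinical procedures or assessments will be required as part of this observational study". After discontinuation, information on clinical management "may be collected whenever available, even after treatment discontinuation".

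**ADR duty.** Section 11 makes the investigator answerable for seeing that all ADRs "that occur after the first administration of Alendronate through the end of study and through the following 6 months are captured". The duty covers events the investigator notices and events the woman herself mentions.

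**Follow-up.** Sections 1 and 8 count about 6 months from the patient's last visit. Section 6 counts from completion of the study, and Section 11 from the end of study. The Section 14 table has a 12-month End of Study column and a 6-month follow-up column in which only ADR and SADR are marked. It has a row for discontinuation and its reasons, but none for BMD, DXA, fractures or radiographs.

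**Analysis.** Section 10 limits every analysis to women who received at least 46 of 48 doses. It leaves missing values missing.

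**The concern.** A woman who stops alendronate without leaving the study no longer has the reason for the monthly visit, and that visit is the route by which ADRs are obtained. The duty to capture her ADRs continues, but only events that the investigator observes or she reports will be captured. No contact is laid down at which either would happen. Her fractures depend in the same way on whether something brings her back to this clinic.

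Stopping is plausibly linked to intolerance or poor response, so this ascertainment would be selective. The fracture and ADR numerators would depend partly on who happened to return. The gap is one of data collection: an analysis set can be redefined later, but events that were never recorded may not be recoverable.

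**Working it through.** **1. The plan's own figure.** Section 10 has n = 1.96² × 0.051 × 0.949 / 0.02² = 464.8, so 465. Then 465 × 1.10 = 511.5, so 512. Both reproduce. The allowance ("If we add 10% to compensate for potential loss of subjects") covers 512 − 465 = 47 women (9.2%). It is not a stopping rate, and the protocol gives none. The present point does not turn on the sample size.

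**2. The provisions side by side, for a woman who stops but stays in the study.**

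| Item | What covers her | What secures it |
|---|---|---|
| ADRs to month 18 | Section 4 objective; Section 11 duty | Monthly visits tied to the prescription; follow-up column with no contact method |
| Fractures to month 12 | Section 4 objective | Available routine information is recorded; no table row |
| Lumbar BMD at month 12 | Section 4 objective | No DXA scheduled, for her or for anyone |

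**3. The follow-up anchor.** For a woman who attends to month 12, all versions agree: 12 + 6 = 18. For a woman whose last prescription visit is at month t, reading last visit literally ends follow-up at t + 6, which is 12 − t months short of month 18. With t = 3, follow-up ends at month 9, which is 9 months short. The text does not say which reading is meant.

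**4. Illustration of exposure.** Assumption: a fraction s = 10% or 30% stops, uniformly over months 0–12 (mean month 6). Planned observation is 512 × 18 = 9,216 person-months.

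- Time after stopping: s × 512 × (18 − 6) = 614 (7%) or 1,843 (20%).
- Time beyond 6 months after stopping: s × 512 × (12 − 6) = 307 (3%) or 922 (10%).

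**5. Illustration for ADRs.** Further assumptions: true 18-month risk 20% and a constant hazard that does not fall after stopping, h = −ln(0.8)/18 = 0.0124 per month. The observed proportion is (1 − s) × 0.20 + s × (stoppers' observed risk).

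- Nothing captured after stopping: stoppers' risk = 1 − (1 − e^(−12h))/(12h) = 7.1%. Observed: 18.7% (s = 10%) or 16.1% (s = 30%).
- Six further months captured: stoppers' risk = 1 − e^(−6h)(1 − e^(−12h))/(12h) = 13.7%. Observed: 19.4% or 18.1%.

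The standard error of a 20% proportion in 512 women is √(0.2 × 0.8/512) = 1.8 points. These proportions are for all 512 women, not for the 46-dose set that the plan would analyse.

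**The case against.** The strongest reply is that the protocol already requires more than the quoted clause suggests. The clause concerns clinical-management information. Elsewhere in Section 8, available routine information, including fracture history and ADRs, is to be recorded in mandatory terms. Section 11 makes ADR capture and SADR reporting mandatory, with no exception for stoppers. Sections 8 and 14 plan an End of Study point and a 6-month follow-up, and Section 14 records discontinuation.

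This stands, and it rules out several stronger readings that a reader might infer:

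- **That the prescription visit is the only planned contact.** It is not. What is missing is a contact method for the other time points and a clear anchor for the follow-up.
- **That ADR collection becomes optional on stopping.** The duty is unconditional; the means of meeting it is unspecified.
- **That month-12 BMD is missing because of the discontinuation clause.** No DXA is required for any woman, and the table has no row for it.
- **That there is no rule for a missing value.** Section 10 has one: no imputation, observed values only.

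A further objection is that the 46-dose rule drops early stoppers from every analysis, so better collection alone would change no reported result. That is correct. It does not remove the point, but the two corrections have to be made together.

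**Conclusion.** The point holds in a limited form and should be corrected. The protocol keeps stoppers under observation and within its objectives and ADR rule. Yet it leaves further information to availability, ties ADR capture to a visit they no longer need, and counts follow-up from an undefined last visit. Selective ascertainment of their fractures and ADRs is a likely result. The month-12 BMD gap is real but applies to all patients.

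No bias size can be taken from the protocol. The figures above rest on an assumed stopping rate, stopping pattern and ADR risk. They also rest on a hazard that persists unchanged after the drug is stopped, which probably overstates the loss. Honouring 6 months of follow-up from the last visit roughly halves the ADR shortfall, from 1.3–3.9 points (20 − 18.7; 20 − 16.1) to 0.6–1.9 points (20 − 19.4; 20 − 18.1).

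A reader might also infer a definite overstatement of the mean BMD gain. If stoppers gained 1.0–2.5% and the others 5.1%, s × (5.1 − gain) gives 0.26–0.41 points at 10% stopping and 0.78–1.23 at 30%. The documents do not support attributing this to the collection wording. The gains are assumed, DXA is unscheduled for everyone, and the 46-dose rule would exclude early stoppers even with complete data.

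**What to change.** - **Section 8:** state that every enrolled woman who has not withdrawn consent stays in follow-up whether or not she still takes alendronate. Record treatment status, fractures and any routine-care lumbar DXA or spine radiograph at months 6 and 12 from initiation. Record ADRs and SADRs to month 18 from initiation. Use medical records or, for ADRs, treatment status and symptomatic fractures only, telephone if she no longer attends.
- **Sections 1, 6, 8 and 11:** count the 6-month follow-up from month 12, not from the last visit.
- **Section 14:** add BMD and fracture rows.
- **Sections 1 and 10:** define the BMD time points as 6 and 12 months after initiation, to match the objectives.
- **Section 10:** adopt an analysis set that does not require 46 doses, at least for safety. Otherwise the added data enter no analysis.

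None of this adds a clinical procedure or changes care. The cost is protocol wording, some extra site time for record checks and calls, and possibly a less favourable reported result. One limit remains: telephone contact cannot supply DXA values or radiographic fractures without symptoms, so these will still be missing where routine care did not produce them.

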9. REMOVAL AND REPLACEMENT OF PATIENTS

Removal of Patients:

Patients have the right to withdraw fully from the study at any time and for any reason without prejudice to her future medical care by the physician or at the institution. Withdrawal of full consent for this study means that the patient does not wish to or is unable to continue further study participation; patient data up to withdrawal of consent will be included in the analysis of the study. The investigator will discuss with the patient appropriate procedures for withdrawal from the study. Should a patient (or a legally acceptable representative) request or decide to withdraw from the study, all efforts will be made to complete and report the observations as thoroughly as possible up to the date of withdrawal. All information should be reported on the applicable eCRFs.

Replacement of Patients:

Participants who withdraw from the study or lost to follow-up will not be replaced.

10. STATISTICAL CONSIDERATIONS

Study Outcomes:

The following outcomes are to characterize/estimate the effectiveness during the first 12 months of treatment with Alendronate.

Primary outcome:

- BMD change (%) at lumbar spine at 6,12 months of treatment measured by DXA

Secondary outcomes:

- the proportion of patients with severe osteoporosis experiencing one or more new vertebral and non-vertebral fragility fractures assessed by spine radiographs regardless of symptoms
- Compliance to therapy, self-reported by patients
- Days lost from work due to fracture-related back pain, self reported by patients

The following secondary outcomes are to characterize the safety of patients during the first 12 months of treatment with Alendronate and during the 6 month follow up period:

- the proportion of patients with ADR to Alendronate
- the proportion of patients with serious ADR to Alendronate

The Full Analysis Set will consist of all enrolled patients satisfying the inclusion/exclusion criteria that receive at least 46 doses - 96% of the 48 that ideally would receive during the study duration- and have a non-missing enrollment date. All analyses will be performed on this analysis set.

Subsets and/or Covariates:

The following variables will be collected at baseline, either directly as part of routine clinical practice, or from medical records when available:

Demographic patient data:

- Educational level
- Patient employment status
- Patient living situation (at home with spouse/family, at home with care/support, at home alone, nursing home)

Medical condition regarding osteoporosis:

- Body mass index (≤ 25 or > 25 kg/m²)
- Age at menopause
- Cause of menopause (natural onset, clinically/surgically induced)
- Height loss since maximal height
- Height loss in centimeters (cm)
- Previous fracture
 - Previous hip fracture
 - Previous vertebral fracture
 - Other previous fractures
- Previous hospitalization for osteoporotic fracture and/or surgical osteoporotic fracture treatment
- One or more falls experienced during the past 12 months
- One or more episodes of immobility experienced during the past 12 months
- Parent fractured hip
- Current smoker
- Former smoker
- Systemic glucocorticoid use
- Secondary osteoporosis
- Alcohol consumption
- Femoral neck BMD T-score
- Lumbar spine BMD T-score
- Total hip BMD T-score

Patient-related:

- Age (years)
- Age group (< 65, ≥ 65 to <75, ≥ 75 years)
- Time since Post Menopausal Osteoporosis (PMO) diagnosis
- Number of comorbidities
- Any chronic medical condition
- Type of chronic medical condition (diabetes/osteoporosis/hypertension/other)

Sample Size:

A review of published data highlighted that BMD change at lumbar spine at 12 months for postmenopausal women on alendronate 70mg weekly ranges from 3.7%-5.1%.¹³⁻¹⁵

Taking into account the most unfavourable result, which is 5.1%, we will estimate the sample size of our study. We will conduct an observational study which intends to investigate the Lumbar Spine BMD (%) change from baseline to 12 months (single proportion).

Published data estimate that Lumbar Spine BMD increases 5.1% from baseline to 12 months.

We would like to ensure that 95% CI of the Lumbar Spine BMD change (%) is estimated with precision ±2% (i.e. with a margin of error of 2%).

The required sample size would be $n \geq \frac{z^2}{\delta^2} p(1-p) \rightarrow n \geq \frac{1.96^2}{0.02^2} 0.051(1-0.051) \rightarrow n \geq 465$

If we add 10% to compensate for potential loss of subjects, the final number will sum up to $n \geq 512$ patients.

Thus in order to have sufficient precision and compensate for potential loss of subjects the final sample size should be 512 patients.

Data Analyses

This is an observational study for which the analysis will be descriptive in nature and no formal hypothesis will be tested. T test will be used to assess the change in BMD between baseline and end of study measurements. Significance was indicated at $P < 0.05$.

For quantitative parameters (BMD, days lost from work) mean, standard deviation, median, range (minimum and maximum), as well as number of missing data (if relevant) will be displayed. For qualitative parameters (bone fractures) counts, percentages and number of missing data if relevant will be displayed. Treatment compliance for each patient will be calculated as the number of doses study drug was actually taken, with the maximum count being 48. Compliance will be regarded as a quantitative parameter.

In general, missing values will remain as missing, i.e., no attempt will be made to impute missing values and only observed values will be used in data analyses and presentations.

Baseline characteristics will be described. Demographics, medical history and other baseline variables will be summarized as appropriate to the type of data.

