5. BACKGROUND

Disease

Osteoporosis is described by the World Health Organization as a 'progressive systemic skeletal disease characterized by low bone mass and microarchitectural deterioration of bone tissue, with a consequent increase in bone fragility and susceptibility to fracture.'¹ Osteoporosis is a major public health threat; in a recent review, the prevalence of osteoporosis was reported as an estimated 200 million people worldwide while about 40 to 50% of women are at risk of having an osteoporotic fracture in their lifetimes.^{2,3}

Nonetheless, most women with osteoporosis remain asymptomatic, which makes epidemiological research especially difficult.⁴ Osteoporosis related fractures are associated with significant morbidity and mortality. Their non-fatal consequences include pain, physical impairment and loss of functional ability, which can have significant adverse effects on patient quality of life. There are also substantial costs to society in terms of diminished activity, hospitalization and lengthy stays in nursing homes as well as days lost from work.⁵

A diagnosis of osteoporosis can be made on the base of either fractures occurring without significant trauma or low bone mineral density measured by dual energy X-ray absorptiometry (DXA).⁶

According to the WHO diagnostic classification, osteoporosis in Caucasian women is defined as a bone mineral density (BMD) at the hip or lumbar spine that lies 2.5 standard deviations or more below the average for the young healthy female population (T-score <-2.5 S.D.).⁶ Osteoporosis can be treated effectively mainly by antiresorptive agents, such as bisphosphonates, by anabolic agents, such as parathyroid hormone analogues, by denosumab which is a fully human monoclonal antibody that inhibits RANKL, by strontium, and by raloxifen a selective estrogen receptor modulator.^{7,8} Other non-pharmacological strategies suggested

to reduce the burden of osteoporosis are smoking cessation and exercise.⁹ Bisphosphonates represent a major advance in osteoporosis treatment and remain at the forefront of medications used for years with great efficacy and safety for the care of patients.¹⁰

Drug background

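### The only listed fracture outcome is confined to an undefined severe-osteoporosis group, while the fracture objective, the analysis set and the analysis text carry no severity limit

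*Protocol*

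**What the plan says.** - **Objective.** Protocol Section 4 sets the secondary objective as: "Evaluate new vertebral and non-vertebral fragility fractures, hip fractures, treatment compliance, occurrence of back pain". It names no severity group. The synopsis states the same objective.
- **Outcome.** Section 10 (Study Outcomes) lists one fracture outcome: "the proportion of patients with severe osteoporosis experiencing one or more new vertebral and non-vertebral fragility fractures", to be read from spine radiographs whether or not there are symptoms. The synopsis repeats it with the same restriction.
- **Population enrolled.** Section 7 admits "Postmenopausal women who are diagnosed with osteoporosis either by a DXA scan with a T score <-2.5 either by suffering a low intensity fracture", the latter "even in the absence of a DXA scan with T score <-2.5". There is no severity grade. Section 5 defines osteoporosis by a T-score threshold and gives no severe category.
- **Baseline data.** Section 10 lists lumbar spine, femoral neck and total hip T-scores, and fracture history including "Previous vertebral fracture". These are taken from routine practice, or from medical records where available.
- **Analysis.** Section 10 runs all analyses on a single Full Analysis Set that is not limited by severity. For bone fractures it plans counts, percentages and the number missing, again without a severity limit.
- **Ascertainment.** Section 8 adds no assessments beyond routine care. The visit table in Section 14 lists no radiograph.

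**The concern.** The objective asks how often treated women have a new fracture. The outcome answers for a subgroup only, and the protocol does not say who is in it. A woman who entered on a T-score alone and then fractures may or may not count, depending on a definition that is not given. The wording also leaves the denominator open: it could be the severe women or all women.

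The proportion could be published as the fracture risk of Greek women on weekly alendronate when it is not that figure. The direction of the error depends on which denominator is used.

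**Working it through.** **The plan's own figure.** The sample size reproduces: 1.96² × 0.051 × 0.949 / 0.02² = 464.82, rounded up to 465; 465 × 1.10 = 511.5, rounded up to 512. It was set for BMD. No figure is stated for fractures, so it neither supports nor contradicts this point.

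**Side by side.**

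| Place in the protocol | Women covered |
|---|---|
| Section 4 and synopsis, fracture objective | no severity limit |
| Section 7, eligibility | T-score or low-intensity fracture, no severity grade |
| Section 10, Full Analysis Set | no severity limit |
| Section 10, Data Analyses, bone fractures | no severity limit |
| Section 10 and synopsis, fracture outcome | severe osteoporosis only, undefined |

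The outcome is the only place with the restriction. It appears in both the synopsis and Section 10, so it is not an isolated slip.

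**Illustrative size.** The protocol gives neither the share of severe women nor any 12-month fracture risk, so both are assumed. Let s be the severe share and R the risk in severe women divided by the risk in the others. Put D = sR + (1 − s). Then:

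- share of women with a fracture who fall outside the outcome = (1 − s) / D
- reported risk / cohort risk, severe women as denominator = R / D
- reported risk / cohort risk, all women as denominator = sR / D

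| s | R | D | Outside the outcome | Ratio, severe denominator | Ratio, all-women denominator |
|---|---|---|---|---|---|
| 0.20 | 1.5 | 1.10 | 73% | 1.36 | 0.27 |
| 0.20 | 3 | 1.40 | 57% | 2.14 | 0.43 |
| 0.30 | 2 | 1.30 | 54% | 1.54 | 0.46 |
| 0.50 | 1.5 | 1.25 | 40% | 1.20 | 0.60 |
| 0.50 | 3 | 2.00 | 25% | 1.50 | 0.75 |

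Over s = 0.20-0.50 and R = 1.5-3, the share outside is 25-73%. The ratio is 1.2-2.1 with the severe denominator and 0.27-0.75 with the all-women denominator.

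**In patients.** Assume 512 women, 40% severe, and risks of 6% (severe) and 3% (others).

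- Severe women with a fracture: 204.8 × 0.06 = 12.3. Others: 307.2 × 0.03 = 9.2. Total 21.5.
- Cohort risk: 21.5 / 512 = 4.2%.
- Outcome as worded: 6.0% with the severe denominator, or 12.3 / 512 = 2.4% with all women.
- Outside the outcome: 9.2 / 21.5 = 43%.
- Approximate 95% half-width, 1.96 × √(p(1 − p)/n): 3.3 percentage points for 6% in 204.8 women, against 1.7 for 4.2% in 512.

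**Edge case.** If R = 1, the severe-denominator percentage equals the cohort's. Even so, 1 − s, that is 50-80% of women with a fracture, stay outside the outcome, and the interval is wider.

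**The case against.** Several parts of the opposing case stand.

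- **Recording.** A reader might infer that the severe group cannot be identified from the study data. The protocol does not support that. No field is labelled severe, but T-scores and previous fractures are on the baseline list, and a SAP, not seen here, could supply a definition. A denominator chosen after seeing the data is therefore a possibility, not something shown.
- **Counting.** A reader might infer that fractures in other women will not be counted at all. Section 10's Data Analyses text plans unrestricted fracture counts, and the outcome on days lost from work because of fracture-related back pain has no severity limit. The protocol is inconsistent; it does not clearly exclude these fractures.
- **Direction.** A reader might infer that the outcome must overstate the cohort risk. That needs severe women as the denominator and a higher risk among them. With all women as denominator it understates.
- **Size.** The illustration rests wholly on assumed inputs. A wider set (20-60% severe, risk 1-3% in the others, ratio 1-4) puts 14-80% outside the outcome.
- **Importance.** This is one secondary outcome in a descriptive study. The BMD outcome and the sample size are untouched.

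What does not stand is leaving the matter to the SAP. A SAP can define severe disease, but the outcome would still cover a subgroup while the objective covers all the women.

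**Conclusion.** The mismatch holds on the text alone. The listed fracture outcome is limited to a group the protocol does not define, while the objective, analysis set and fracture summaries carry no such limit. As written it does not answer the objective, and its denominator is ambiguous.

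The distortion cannot be computed from the protocol. The illustrative 25-73% of women with a fracture outside the outcome assumes 20-50% severe and a risk ratio of 1.5-3; the 1.2-2.1 times the cohort risk further assumes severe women as denominator. It should be fixed, at a priority suited to a secondary, descriptive outcome.

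**What to change.** 1. In Sections 1 and 10, delete the restriction to severe osteoporosis from the fracture outcome and name all women in the analysis set as the denominator, to match Section 4.
2. If the severe group is of interest, report it in addition, as a subgroup defined in advance from the baseline T-scores and previous fractures already listed. Show women who lack the needed items as not classifiable.
3. Report how many women have follow-up spine radiographs, and show those without as missing. Section 8 adds no assessments and Section 14 lists no radiograph, so nothing guarantees complete ascertainment in the whole cohort.

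**Cost.** The outcome wording changes in two places, and the subgroup needs a short definition. No additional patients are needed. It should not be presented as free of data problems: the whole-cohort proportion may rest on incomplete radiographs. It will probably also be lower than the severe-only figure, if severe women fracture more often.
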